1.2.4 MRD as Clinical Outcome in Myeloma Patients

MRD testing in NDMM patients following first-line therapy was originally developed using multi-color flow cytometry,²⁵ which has been widely used in several trials for multiple myeloma.^{26,27} Due to their superior sensitivity, genomic testing like Next Generation Sequencing (NGS) or IgH became the preferred method of MRD testing. Specifically, flow cytometry-based MRD assays can detect 1 myeloma cell in 100,000 bone marrow cells; current genetic MRD assays can detect 1 myeloma cell in 1,000,000 bone marrow cells.²⁸ This is important because the depth of MRD correlates with PFS.^{29,30,31,32} Data are limited in patients with high-risk myeloma but also show that MRD is an independent risk factor in high-risk myeloma.³³ Therefore multiple expert reviews propose that MRD testing should and will become a primary regulatory efficacy endpoint.^{3,22,34}

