1.2.7 Rationale for use of MRD testing as Primary Endpoint

As stated above, MRD is strongly correlated with the gold standard of PFS, which can take over 2 years to reach even in a high-risk myeloma patient population with the use of novel agents. Demonstrating MRD negativity in the context of safety and other endpoints therefore will be highly informative in assessing Descartes-11 for treatment of high-risk NDMM patients. In the era of novel agents, sCR rate in high-risk NDMM patients is reported to be 10% after induction treatment, 20% after ASCT and 50% after 3 years of RVD.²³ Similarly, CR was seen in less than 10% of high-risk patients post-induction, 20% of patients after ASCT and 50% after 2 years of bortezomib maintenance in the HOVON trial.¹⁹ Finally, the large PETHEMA trial using bortezomib/immunomodulatory drug combination reported 35% CR rate in high-risk patients following transplant. In a smaller series in which 25% of the patients were high risk, investigators tested proteasome inhibitor-based combination as an induction therapy followed by ASCT and reported MRD-negative CR in 20% of the patients after transplant.¹⁷ To our knowledge there is only one reported study that investigates the impact of each phase of treatment onto the depth of response which used flow cytometry for MRD assessment and showed that following induction therapy 1%, after first transplant 0.24% and after second transplant 0.1% of the cells were abnormal.⁶³ The greatest MRD negativity reported for high-risk patients in a small series (5 patients) in which 44% of the patients achieved MRD negativity after 8 cycles of carfilzomib, lenalidomide and dexamethasone combination which did not deepen after ASCT or 1 year of lenalidomide maintenance.⁶⁴ Thus, achieving more than 20% MRD negativity pre-ASCT in patients receiving bortezomib based regimen or 50% in all newly diagnosed patients after completing frontline therapy will be a significant improvement in NDMM with high-risk features. In this protocol, bone marrow will be evaluated by IgH/IgK gene rearrangements to search for MRD up to 1 in 10^5 cells.

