2.1 Eligibility Criteria

2.1.1 Inclusion Criteria

The following inclusion criteria will be applied at Screening, unless another evaluation time point is specified:

1. High-risk multiple myeloma patients (defined below) who complete pre-transplant induction treatment anti-myeloma drug combination (minimum 2 drugs).
2. Following completion of the pre-transplant induction regimen, patients must have residual disease measured by at least one of the following markers:
 - a. Serum M-protein detectable by immunofixation
 - b. Urine M-protein detectable by immunofixation
 - c. Abnormal FLC ratio
 - d. A biopsy-proven plasmacytoma or residual disease on imaging of a spot that was known to have plasmacytoma
 - e. Evidence of clonal cells in immunohistochemistry defined as Kappa/Lambda <4:1 or >1:2 after counting ≥ 100 plasma cells
 - f. Evidence of MRD detected by DNA-based or flow cytometry approaches
3. Patients must have high-risk multiple myeloma based on IMWG consensus as defined by R-ISS Stage III¹⁰ or high-risk CA³.
 - a. R-ISS Stage III is defined as having serum β -microglobulin ≥ 5.5 mg/L and either a high risk CA by iFISH or high LDH.
 - b. High-risk CAs are defined as having 1) t(4;14), t(14;16), t(14;20), or del(17/17p) in at least 20% of the cells; 2) any non-hyperdiploid karyotype, 3) gain(1q); 4) del 13; 5) gain 1q; or 6) a high-risk signature on gene expression profile (GEP).
4. There should be at least 7 days between the last dose of anti-myeloma drug and first Descartes-11 infusion.
5. Toxicities from prior therapies must have resolved to Grade 2 or less according to the CTCAE 5.0 criteria, or to the subject's pre-therapy baseline at the time of first cell infusion.
6. Patients must have signed written, informed consent.
7. Patients must be 18 years of age or older at the time of enrollment.
8. Patients must have clinical performance status of ECOG 0-2.
9. Patients must be seronegative for HIV.
10. Patients must be seronegative for hepatitis B (HBV) antigen; or, if the patient is positive for the hepatitis B antigen test, he or she must be negative for HBV DNA and must agree to use Hepatitis B prophylaxis as per institution guideline and/or principal investigator discretion.

11. Patients must be seronegative for hepatitis C (HCV) antibody; or, if the hepatitis C antibody test is positive, the patient must be tested for the presence of viremia by RT-PCR and must be HCV RNA negative.

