4.1.3 Safety and Response Assessment Visit (Day 28 ± 3 days)

During the visit, the following assessment must be completed:

1. Medical history for adverse events
2. Vital signs including pulse oximetry, weight and physical exam including brief neurological exam
3. ECOG performance status
4. Concomitant medications
5. Complete blood count, differential
6. Chemistry panel (Glucose, Ca, Mg, Phos, Albumin, Total Protein, Total Bilirubin, K, Na, Cl, HCO₃, BUN, Cr, ALT, AST, lactate dehydrogenase)
7. Urinalysis

8. Urine pregnancy test for all women of child-bearing potential
9. CRP, ferritin
10. Research blood (See Laboratory Manual for collection details)
11. If present at baseline, serum protein electrophoresis (SPEP), serum immunofixation electrophoresis (SIFE)
12. If present at baseline, 24-h urine for total protein, urine protein electrophoresis (UPEP), urine immunofixation electrophoresis (UIFE)
13. If present at baseline, serum free light chain (FLC) assay
14. β 2- microglobulin
15. If required for depth-of-response evaluation based on peripheral markers, then unilateral bone marrow aspirate + biopsy, including bone marrow immunohistochemistry and bone marrow flow cytometry. MRD assessment (with NGS) is performed if patient is in sCR.
16. Imaging of a previously known plasmacytoma if already imaged at baseline visit

4.1.4 Follow-up Months 1, 3, 6, 9, 12, 18, 24, 36 (\pm 2 weeks)

1. Medical history for adverse events
2. Current medical conditions and physical examination (including weight, vital signs, pulse oximetry)
3. ECOG performance status
4. Concomitant medications
5. Complete blood count, differential
6. Chemistry panel (Glucose, Ca, Mg, Phos, Albumin, Total Protein, Total Bilirubin, K, Na, Cl, HCO₃, BUN, Cr, ALT, AST, lactate dehydrogenase)
7. Urinalysis
8. If present at baseline, serum protein electrophoresis (SPEP), serum immunofixation electrophoresis (SIFE)
9. If present at baseline, 24-h urine for total protein, urine protein electrophoresis (UPEP), urine immunofixation electrophoresis (UIFE)
10. If present at baseline, serum free light chain (FLC) assay
11. β 2- microglobulin

Additional notes:

- If required for depth-of-response evaluation based on peripheral markers, then unilateral bone marrow aspirate + biopsy, including bone marrow immunohistochemistry and bone marrow flow cytometry. MRD assessment (with NGS) is performed if patient is in sCR.
- Imaging of a previously known plasmacytoma if already imaged at baseline visit

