5.5 Stopping Rules and Study Termination

Premature termination of the clinical trial may occur because of a regulatory authority decision, change in opinion of the IRB or medical monitor. Additionally, recruitment may be stopped for reasons of particularly low recruitment, protocol violations, or inadequate data recording. Specifically, study will be stopped if:

- Study Sponsor or a Regulatory Body decides for any reason that subject safety may be compromised by continuing the study.
- The Sponsor decides to discontinue the development of the intervention to be used in this study.

The study will be **paused if:**

- There is death that is reasonably attributed to study drug within the first 30 days after first infusion
- Two subjects with Grade 4 adverse events to vital organs that are assessed as probably or definitely related to study drug within the 14 days after last infusion

If the study is paused for the reasons above, the PI and members of the study team will meet in person or by teleconference within 24 hours of the event to have a thorough discussion of the event. Meeting minutes capturing the review of any ongoing investigations, including next steps in the management of the subject and any proposed changes to the protocol will be forwarded to the medical monitor. If all parties agree as to the event resolution, then the pause will be lifted. If the study is paused for manufacturing reasons, the Sponsor will make recommendations for process improvements to be implemented. Pending successful completion of a process validation run, the manufacturing pause will be lifted.

6 Statistical Considerations

Statistical analysis will be described in a separate Statistical Analysis Plan.

Briefly, with respect to sample size: the primary endpoint will be the proportion of responders, i.e., patients who are MRD-negative with sCR at the Day 28 Visit. This is an open-label study, and the null hypothesis is that the responder rate will not differ from the natural rate of MRD-negative sCR at the end of consolidation, as observed in the literature. We determined that this natural rate is 10%.^{19,31,64,69-73} For purposes of power calculations, we assume that the response rate will be 35%. With these assumptions, a sample size of 34 will provide 80% power to detect a one-tailed difference at the 95% confidence level.

7 Ethical Considerations

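### Criterion 2f sets no lower limit on DNA-based MRD, so a patient admitted on MRD below 1 in 10^5 alone could count as a Day 28 responder with no change in disease

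*Combined protocol and SAP*

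**What the plan says.** **Entry.** Under Section 2.1.1, item 2, "patients must have residual disease measured by at least one of the following markers". One marker is enough, and item 2f is "Evidence of MRD detected by DNA-based or flow cytometry approaches". It names no assay, depth or lower limit.

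**Assay depth in general.** Section 1.2.4 states that "flow cytometry-based MRD assays can detect 1 myeloma cell in 100,000 bone marrow cells" and that "current genetic MRD assays can detect 1 myeloma cell in 1,000,000 bone marrow cells".

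**Depth in this trial.** Section 1.2.7 ends: "In this protocol, bone marrow will be evaluated by IgH/IgK gene rearrangements to search for MRD up to 1 in 10^5 cells". No other section gives a depth for the trial's own MRD testing.

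**Endpoint.** Section 6 defines responders as "patients who are MRD-negative with sCR at the Day 28 Visit", with no reference to a baseline MRD value. Section 4.1.3 adds only that "MRD assessment (with NGS) is performed if patient is in sCR".

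**Screening.** The marrow work-up in Section 4.1.1 consists of immunohistochemistry and flow cytometry. No DNA-based MRD test is listed.

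**The concern.** Entry and endpoint may be judged at different depths. Suppose a patient's only residual-disease marker is a DNA-based result of 4 in 10^6. That result satisfies 2f. If the Day 28 test looks no deeper than 1 in 10^5, the same tumour load reads as negative.

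The sCR requirement does not protect against this. A patient who qualifies on 2f alone has, by construction, none of the markers in 2a to 2e: immunofixation is negative in serum and urine, the free light chain ratio is normal, there is no plasmacytoma, and immunohistochemistry shows no clonal cells (taking 2e by its evident intent). Those are the sCR components in Table 1, apart from fewer than 5% plasma cells in the aspirate. The patient in effect brings the sCR half of the endpoint to the trial, and the difference in depth could supply the other half.

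At stake is the single-arm test against a fixed 10%. It has no control arm in which the same artefact would show up, and few responders are needed to reject.

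**Working it through.** **Inputs.** From Section 6: n = 34, null rate 10%, assumed rate 35%, one-sided 5% level, 80% power. The number k of patients who enter by this route is not in the documents. It is an assumption, shown here from 0 to 3.

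**Step 1: the plan's own figure.** The two-sample, per-arm formula, one-sided and without continuity correction, is
[1.645 × √(2 × 0.225 × 0.775) + 0.842 × √(0.10 × 0.90 + 0.35 × 0.65)]² / 0.25² = 33.4, which rounds up to 34. So 34 reproduces, but from a two-arm formula. That is a separate matter. The check below uses the exact single-arm test that Section 6 describes.

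**Step 2: the rejection rule.** Write T(m, r) for P(X ≥ r) with X ~ Binomial(m, 0.10). T(34, 6) = 11.9% and T(34, 7) = 4.8%, so the one-sided 5% test rejects at 7 or more responders. Power at 35% is 97.8%.

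**Step 3: k patients certain to score as responders.** The other 34 − k respond at 10%. The chance of rejecting with an ineffective drug is T(34 − k, 7 − k):
- k = 1: T(33, 6) = 10.6%
- k = 2: T(32, 5) = 21.1%
- k = 3: T(31, 4) = 37.6%

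**Step 4: each keeps that status only with probability 0.5 (an assumption).** The chance is the sum over j = 0 to k of C(k, j) × 0.5^k × T(34 − k, 7 − j):
- k = 1: 0.5 × 0.0417 + 0.5 × 0.1061 = 7.4%
- k = 2: 0.25 × 0.0358 + 0.5 × 0.0944 + 0.25 × 0.2115 = 10.9%
- k = 3: 0.125 × 0.0306 + 0.375 × 0.0834 + 0.375 × 0.1932 + 0.125 × 0.3762 = 15.5%

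| Patients entering this way | All keep status | Each with probability 0.5 |
|---|---|---|
| 0 | 4.8% | 4.8% |
| 1 | 10.6% | 7.4% |
| 2 | 21.1% | 10.9% |
| 3 | 37.6% | 15.5% |

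**Step 5: how many are plausible.** Section 1.2.7 cites sCR in 10% of high-risk patients after induction, which is 0.10 × 34 = 3.4 patients before any selection. Three such patients would therefore need nearly all of them to have entered on a DNA-based result inside one tenfold window. The same section cites about 1% abnormal marrow cells after induction in one flow study, which is 10^-2 / 10^-5 = 1,000 times the upper edge of the window. Zero or one is better supported than three, although selective referral could change that.

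**The case against.** The strongest reply is that the mismatch is inferred. The 1 in 10^6 figure is background on assays in general, not a specification of the entry test. The 1 in 10^5 sentence stands in a rationale section, is a search depth rather than a declared negativity threshold, and is not confined to Day 28, so it can be read as covering every MRD test in the trial. Table 2 treats any clonal plasma cells found by next-generation flow or sequencing as loss of MRD negativity, with no depth attached. Section 6 refers the analysis to a separate SAP whose text is not in the document set and which could set a cut-off. On the tests that screening does schedule, the depths match, because flow is put at 1 in 10^5.

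Much of this stands. A reader might infer that the protocol fixes the endpoint at 1 in 10^5 and so makes these patients responders. The documents do not go that far: such a patient could be counted, not must be. The route needs a DNA-based result from outside the screening schedule. A patient in the same MRD range who also has, say, M-protein is not affected until that clears. Nor need status persist: Section 3.2.1 requires at least 7 days off anti-myeloma drugs before the first infusion, and high-risk disease may move by Day 28.

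What does not fall is the wording of 2f. It accepts a DNA-based result of any depth from any source, the general 1 in 10^5 statement does not limit it, and Section 6 as written requires no fall from a baseline value. A cut-off in the SAP would not change the entry criterion.

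**Conclusion.** The point holds in a narrow form. Criterion 2f, Section 1.2.7 and Section 6 together allow a patient admitted solely on DNA-based MRD between 1 in 10^6 and 1 in 10^5 to be counted as a responder with unchanged disease. The flow route is not affected.

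The percentages above are illustrations, not expected error rates. They assume a number of patients that the documents do not give, a 10% response rate in everyone else, and a stated chance of keeping the same status. With no such patients the error stays at 4.8%. A reader might infer that the trial's type I error is inflated to between 10.6% and 37.6%. The documents do not support that, since the count may be zero. A reader might also conclude that 1 in 10^5 is the wrong threshold because Section 1.2.4 prefers genomic tests for their sensitivity. The choice of depth is the sponsor's; the weakness is that it is not tied to both ends of the comparison.

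It is still worth correcting: with a cut-off of 7, one such patient who keeps that status raises the error from 4.8% to 10.6%, and the correction is small.

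**What to change.** State one MRD cut-off, 1 in 10^5 as in Section 1.2.7, for both entry and endpoint.

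- **Criterion 2f:** when MRD is the only residual-disease marker, require a DNA-based or flow result at or above that cut-off.
- **Section 6 and SAP:** count a patient who entered on MRD alone as a responder only if the entry result was at or above the cut-off and the Day 28 result is below it.

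A new baseline sequencing assay should not be made a condition. It would add a test that screening does not schedule and would stop flow alone from qualifying a patient, which 2f now allows. A supplementary Day 28 rate at 1 in 10^6 makes sense only if the assay used reaches that depth, which the protocol does not say.

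The cost is a line in 2f and a line in Section 6 and the SAP, with no new sample. The downside is that a few patients with very low MRD become ineligible or stop counting as responders, so the observed rate may be slightly lower.

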2.1.2 Exclusion Criteria

The following exclusion criteria will be applied at the time of Screening, unless another evaluation timepoint is specified:

1. Patients who are pregnant or lactating.
2. Patients who have any active and uncontrolled infection. No blood cultures are necessary unless clinically indicated.
3. Use of any of the following:
 - a. Monoclonal antibody based anti-myeloma treatment prior to Descartes-11 infusion
 - b. Experimental anti-myeloma agents prior to Descartes-11 infusion (off-label use of other FDA-approved anti-myeloma medications is allowed)
4. Ongoing treatment with the following immunosuppressants: calcineurin inhibitors (i.e. tacrolimus), mTOR inhibitors (i.e. sirolimus)
5. Patients who have active central nervous system disease.
6. Patients with second malignancies in addition to MM are not eligible if the second malignancy has required treatment within the past 3 years or is not in complete remission. There are three exceptions to this criterion are successfully treated 1) non-metastatic basal cell 2) squamous cell skin carcinoma, or 3) prostate cancer that has not required anticancer therapy.
7. Active cardiac arrhythmias, active obstructive or restrictive pulmonary disease. If there is a history of cardiac or pulmonary morbidities, the principal investigator will judge whether these conditions are active or in stable condition.
8. Any form of primary immunodeficiency (such as Severe Combined Immunodeficiency Disease).
9. History of severe immediate hypersensitivity reaction to any of the agents used in this study.

10. Subjects who have had a venous thromboembolic event (e.g., pulmonary embolism or deep vein thrombosis) requiring anticoagulation and who meet any of the following criteria:

- Deep venous thrombosis occurred within the past 3 months OR pulmonary embolism occurred within the past 6 months
- If on anticoagulation, based on PI discretion, anticoagulation cannot be withheld and postponed during leukapheresis
- Have had at least Grade 2 hemorrhage in the last 30 days
- Are experiencing continued symptoms from their venous thromboembolic event (e.g. continued dyspnea or oxygen requirement)

2.2 Screening, Evaluation and Enrollment

2.2.1 Recruitment of Patients

Subjects will be identified through the clinical practices of the investigator or sub-investigators and through referrals from outside hospitals and physicians. Patients diagnosed with high-risk multiple myeloma can be referred any time after they complete induction therapy. Patient should be enrolled and treated with Descartes-11 prior to ASCT if they are transplant eligible. If the patient does not have cells available at the time of screening (See [Section 3.3.1.1](#) for details), they can be referred to Sponsor's Cell Collection Protocol (See [Appendix B](#)).

2.2.2 Screening Evaluation

Please refer to [Section 4.1.1](#) for Screening visit evaluations.

2.2.3 Enrollment

To enroll a subject on this study, the following documents are required:

- Copy of signed/dated consent and HIPAA Authorization
- Source documentation to confirm enrollment/eligibility

2.2.4 Early Withdrawal of Subjects

Patients who do not complete at least one Descartes-11 infusion will be considered to have prematurely discontinued the study. The reasons for premature discontinuation must be recorded on the case report form. Final study evaluations will be completed at the time of discontinuation. Provided that all protocol requirements are satisfied for the trial to continue safely, patients who withdraw early from the study will not be counted toward study recruitment limits.

[figure not shown]
2.2.5 Data Collection and Follow-Up of Early Withdrawals

Patients who withdraw early from the study and who have provided consent for follow-up data collection will be eligible for continued data collection for up to one year. Withdrawn patients who are followed at other institutions or practices, because of preference or geographical concerns, will confer follow-up via notes from their local physician and/or phone interviews. Toxicity and other clinical assessments will be obtained from the treating physician and recorded into appropriate case report form (CRF). In the event a subject fails to complete the follow-up requirements, all attempts to contact the subject including: 1) at least three telephone contacts (on different days and at different times of the day), and 2) a certified letter will be documented.

3 Study Design

3.1 Study Schema

Figure 1. Study Schema

[figure not shown]

3.2 Study Implementation

[figure not shown]
3.2.1 Overall Treatment Design

The overall schedule of treatment for this Phase II study is illustrated in [Figure 1](#). Steps shown prior to Screening affect eligibility but are not part of the study.

Eligible patients will receive an induction regimen with at least 2 anti-myeloma agents excluding monoclonal antibodies. After completion of the full pre-transplant induction regimen prior to high-dose chemotherapy and ASCT, eligible patients must have measurable residual disease as defined in the Eligibility Criteria. A patient can be screened and enrolled at that point.

Descartes-11 treatment will begin at least 7 days after the patient's final dose of anti-myeloma therapy. The dose of cells will be 25×10^6 cells/kg, and doses will be given on Days 1, 4, 8, 11, 15, 18 (i.e., total dose of 150×10^6 cells/kg). Weight obtained during Screening Visit will be used for dose calculation. Doses are expressed as the number of live CAR+ cells.

After completing all cell infusions, the patient will be evaluated for clinical response and then followed-up for up to 36 months unless they meet off-study criteria outlined in [Section 4.5.2](#). During the follow-up period, if indicated, any additional induction therapy, high-dose chemotherapy and/or ASCT may be administered at the discretion of the investigator. Except for experimental agents that are not approved for myeloma treatment, treatment will be left to the investigator's discretion. The patient will be followed every 3 months for the first year, every 6 months for the second year and one time during the third year.

